Appendix A. Patient Pre-Implementation & Post-Implementation Questionnaires

[Interviewer reads each question and answer options to the participant, and records their response on this document. Interviewer can repeat questions and answer options as needed, and answer participants' general questions, but should not provide additional information that would alter the participant's response.]

1.1 Perceived Kidney Disease Self-Management Scale + Self-efficacy Scale for Vascular Access Process

We would like to know how much you agree or disagree with the following statements about your kidney disease. For each statement, please choose a number between 1 (strongly disagree) and 5 (strongly agree).

1. It is difficult for me to find effective solutions to problems that occur with managing my kidney disease.
a. Choices: 1 2 3 4 5
 Strongly disagree Somewhat disagree Neutral Somewhat agree Strongly agree

2. I find efforts to change things I don't like about my kidney disease are ineffective.
a. Choices: 1 2 3 4 5
 Strongly disagree Somewhat disagree Neutral Somewhat agree Strongly agree

3. I handle myself well with respect to my kidney disease.
a. Choices: 1 2 3 4 5
 Strongly disagree Somewhat disagree Neutral Somewhat agree Strongly agree

4. I am able to manage things related to my kidney disease as well as most other people.
a. Choices: 1 2 3 4 5
 Strongly disagree Somewhat disagree Neutral Somewhat agree Strongly agree

5. I succeed in the projects I undertake to manage my kidney disease.
a. Choices: 1 2 3 4 5
 Strongly disagree Somewhat disagree Neutral Somewhat agree Strongly agree

6. Typically, my plans for managing my kidney disease don't work out well.
a. Choices: 1 2 3 4 5
 Strongly disagree Somewhat disagree Neutral Somewhat agree Strongly agree

7. No matter how hard I try, managing my kidney disease doesn't turn out the way I would like.
a. Choices: 1 2 3 4 5
 Strongly disagree Somewhat disagree Neutral Somewhat agree Strongly agree

8. I'm generally able to accomplish my goals with respect to managing my kidney disease.
a. Choices: 1 2 3 4 5
 Strongly disagree Somewhat disagree Neutral Somewhat agree Strongly agree

We would like to know how confident you feel about things involved with getting a dialysis vascular access. For each question, please give an answer between 1 and 10, where 1 is “not at all confident”, and 10 is “totally confident”.

1. How confident do you feel completing the steps involved in getting a dialysis vascular access?

Not at all | | | | | | | | | | Totally
Confident 1 2 3 4 5 6 7 8 9 10 Confident

2. How confident do you feel that you know who to go to for questions about vascular access?

Not at all | | | | | | | | | | Totally
Confident 1 2 3 4 5 6 7 8 9 10 Confident

3. How confident do you feel that you understand the importance of getting a vascular access?

Not at all | | | | | | | | | | Totally
Confident 1 2 3 4 5 6 7 8 9 10 Confident

1.2. Vascular Access Knowledge Questionnaire

We would like to understand what you know about vascular access. Please answer the next questions the best you can based on what you know now.

1. What does a vascular access do? [*correct answer=it makes a way for your blood to get to the hemodialysis machine*]
 - a. It helps you figure out what you can eat and drink when you start hemodialysis
 - b. It makes a way for your doctor to know how well your kidneys are doing
 - c. It makes a way for your blood to get to the hemodialysis machine
 - d. Don't know

2. What are the 3 kinds of vascular access for hemodialysis? [*correct answer= fistula, graft, catheter*]

[Interviewer asks participant to name the 3 kinds of vascular accesses. Interviewer does not read off the response options. Interviewer records participant's responses below by circling each of the vascular accesses they name correctly, and writing any incorrect responses under "other".]

- a. Fistula
 - b. Graft
 - c. Catheter
 - d. Other: _____
 - e. Don't know
-
3. What kind of vascular access can get infected most easily? [*correct answer= catheter*]
 - a. Fistula
 - b. Graft
 - c. Catheter
 - d. Don't know

4. What kind of vascular access usually lasts the longest? *[correct answer= fistula]*
 - a. Fistula
 - b. Graft
 - c. Catheter
 - d. Don't know

5. Who picks the kind of vascular access and where it will go on the body? *[correct answer= kidney doctor, patient, and surgeon together]*
 - a. Kidney doctor only
 - b. Patient only
 - c. Surgeon only
 - d. Kidney doctor, patient, and surgeon together
 - e. Don't know

6. Vein mapping helps you figure out the best place on your body for your access. *[correct answer= true]*
 - a. True
 - b. False
 - c. Don't Know

7. Vein mapping happens after vascular access surgery. *[correct answer= false]*
 - a. True
 - b. False
 - c. Don't Know

8. A fistula is ready to be used for dialysis (in other words, ready to be stuck with a needle for dialysis) within one week after it is made. *[correct answer= false]*
 - a. True
 - b. False
 - c. Don't Know

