GHS trained research staff will administer questionnaires to patient and provider/clinic personnel participants. We will obtain verbal or written informed consent prior to enrolling participants in the study. Following screening, recruitment and consent procedures, trained GHS research staff will administer pre-implementation questionnaire questions to participating patients in person (at a previously scheduled, routine clinical appointment or at a time and location of their choosing) or over the telephone (**Appendix A**). Questionnaire administration will not disrupt routine clinical care. Similarly, following screening, recruitment and consent procedures, trained GHS research staff will administer the pre-implementation questionnaire questions to participating providers and clinic personnel at a time that does not interfere with their professional duties in person or over the telephone (**Appendix B**).

The patient and provider/clinic personnel questionnaire questions will take approximately 10 minutes to complete. For both telephone and in person administration of the questionnaires, interviewers will read the questions exactly as written and the response choices for each question. Participants may refuse to answer any question(s). The number of incomplete questionnaires will be monitored.

Patient and provider/personnel participants will also be asked to complete a demographic card (**Appendices C & D**). Patient demographic information collected will include: sex, age, race, ethnicity, education level, and income level. Provider/personnel demographic information collected will include: sex, age, race, ethnicity, professional role, time worked in role at Geisinger and total, and time worked with chronic kidney disease patients, dialysis patients, and with patients going through the vascular access creation process.

At the conclusion of the quality improvement program, trained GHS research staff will administer the post-implementation questionnaire questions to participating patients in person (at a previously scheduled, routine clinical appointment or at a time and location of their choosing) or over the telephone and to participating providers/clinic personnel at a time that does not interfere with their professional duties in person or over the telephone. Questionnaire administration will not disrupt routine clinical care.

Remuneration

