There will be no cost to study participants. Patient participants will receive \$25 total remuneration for pre- and post-implementation questionnaires. Participants electing to terminate the questionnaire early will receive the full amount. A \$10 gift card will be given to patient participants for pre-implementation questionnaires, and a \$15 gift card will be given to patient participants for post-implementation questionnaires. A compensation letter will accompany the remuneration.

DATA ANALYSIS AND POWER

Data Collection Variables

See research pre-/post-intervention questionnaires for data collected from patient and providers (**Appendices A & B**).

Data Collection

Table 1 provides an overview of the data to be collected. The outcomes are patient and provider vascular access-related confidence (self- efficacy) and patient vascular access knowledge. Patient confidence will be evaluated using a questionnaire with 11 total items (3 research team-developed questions and 8 Perceived Kidney Disease Self-Management Scale questions (a validated scale).(7) Patient knowledge will be evaluated using an 8-item research team-developed questionnaire. Provider confidence will be evaluated by an 11-item research team-developed questionnaire.

Table 1. Data Collection Variables.

Outcomes	Pre-Implementation	Post-Implementation
Patient confidence navigating the vascular access creation process (self-efficacy)	X	X
Patient vascular access knowledge	X	X
Provider confidence helping patients navigate the vascular access creation process (self-efficacy)	X	X
Demographics		
Patient age, sex, ethnicity, race, education level, income level	X	
Provider age, sex, ethnicity, race, professional role, time worked in role at GHS and total, and time worked with CKD patients, dialysis patients, and patients going through the vascular access creation process	X	

Data Analysis

Pre- and post-implementation confidence and knowledge measures scores will be calculated according to measure scoring instructions (kidney disease self-management: mean of 8 items,(7) patient vascular access process confidence: mean of 3 items, patient vascular access knowledge: mean of 8 items, provider confidence: mean of 11 items). We will use a paired sample student's t-test to compare pre and post-test score means. Analyses will be performed in SAS v9.4 and R v3.3.2 or later.

RISKS AND DISCOMFORTS

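### Knowledge item 2 is marked live, by staff who will in practice know the time point, and accepted answers keep no wording, so lenient post-program marking could not be re-marked against a strict key

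*Protocol*

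**What the plan says.** Item 2 asks the patient to name the three kinds of vascular access. The form instructs: "Interviewer does not read off the response options". The other seven items are multiple choice or true/false. The key for item 2 is "correct answer= fistula, graft, catheter", with no rule for synonyms, descriptions or near-misses. Answers are recorded "by circling each of the vascular accesses they name correctly, and writing any incorrect responses under" an 'other' line.

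Appendix A has the interviewer read the questions and says that the interviewer "records their response on this document". Monitoring and Quality Assurance says paper forms are scanned and saved before shredding.

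Under Study procedures, after consent "trained GHS research staff will administer pre-implementation questionnaire questions to participating patients in person" or by telephone. Later, "At the conclusion of the quality improvement program, trained GHS research staff will administer the post-implementation questionnaire questions". Neither the protocol nor the SAP describes masking to time point, a second coder or audio recording.

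Data Analysis defines the outcome as "patient vascular access knowledge: mean of 8 items" and compares pre and post means with a paired t-test. It does not say how an item is scaled, or whether naming one or two of the three access types earns part credit. The SAP adds nothing on marking.

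**The concern.** Some patients may answer item 2 in lay or partial terms (for illustration: shunt, port, a tube in the neck). The interviewer must decide on the spot whether such an answer counts. Someone who knows that the patient has just been through an education program may accept a vague answer that would have been refused at baseline. The score would then rise without any learning, in the direction that Aim 1 hypothesises, in a design with no control group to absorb the shift.

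The recording rule makes this harder to audit. Rejected wording is written down, so over-strict marking can be reviewed. Accepted wording is not, so over-lenient marking cannot be reviewed answer by answer.

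**Working it through.** The documents give no SD, effect size, alpha or power, so there is no plan figure to reproduce. This is a size check only.

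**From the documents.** Eight items averaged, so item 2 carries 1/8 = 0.125 of the score if each item runs from 0 to 1. If each of the three terms earned one-third credit, one term would be worth 1/24 = 0.0417. Up to 40 patients (Sample Size).

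**Assumed.** 30-60% of patients give one borderline term; acceptance is 20-40 percentage points higher at post; SD of the paired change is 0.20 on the 0-1 score; two-sided 5% test; no true change.

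**Shift in the mean** = share borderline × difference in acceptance × credit.
- Full item credit: 0.3 × 0.2 / 8 = 0.0075; 0.6 × 0.4 / 8 = 0.03.
- One-third credit: 0.3 × 0.2 / 24 = 0.0025; 0.6 × 0.4 / 24 = 0.01.

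**Standard error** with 40 pairs = 0.20 / √40 = 0.0316.

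**False-positive rate** from the noncentral t with 39 df and noncentrality shift/SE:

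| Credit | Shift | Shift/SE | Rate |
|---|---|---|---|
| One-third | 0.0025 | 0.08 | 5.1% |
| One-third | 0.01 | 0.32 | 6.1% |
| Full item | 0.0075 | 0.24 | 5.6% |
| Full item | 0.03 | 0.95 | 15.2% |

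**Sensitivity of the upper full-credit figure (shift 0.03).** At SD 0.20 it falls to 12.5% with 30 pairs and 9.8% with 20. With 40 pairs it is 23.5% at SD 0.15 and 11.5% at SD 0.25.

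**Sensitivity of the upper one-third-credit figure (shift 0.01).** With 40 pairs it is 7.0% at SD 0.15 and 5.7% at SD 0.25.

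**Could marking alone reach significance?** With 40 pairs and SD 0.20, the smallest significant mean change is 2.023 × 0.0316 = 0.064. Dividing by 0.125 gives 0.51, so about half the patients would need undeserved full credit at post only. The corresponding share is 38% at SD 0.15 and 64% at SD 0.25.

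**The case against.** The discretion is narrow. The key is three specific words, and read plainly the instruction sends a description such as a tube in the neck to the 'other' line. The interviewers are described as trained. Nothing in the documents shows that marking will be lenient, or more lenient at post. This stands, and it is a reason to expect a small effect.

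The size rests on inputs that the documents do not give, and full credit is the least favourable case. Under all-or-none scoring, accepting one vague term changes the score only if the other two terms are also credited, so share × difference overstates the number of patients affected. Under per-term scoring the rate stays near nominal. Forty complete pairs is also the maximum. All of this stands, so the full-credit figures are upper bounds for the assumed inputs.

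Knowledge of the time point is an inference. It is a fair one: staff give one form after consent and the other at program end, and no masking is described.

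A reader might infer that lenient post-program marking could be neither seen nor corrected. The documents do not support that. The bias needs borderline terms to be refused at pre and accepted at post, and the refused ones are exactly those written down. They could be counted, and credited at both time points under one lenient list, which would largely remove the difference. Because accepted wording is lost, nobody could confirm that the list is as wide as the most generous marking. A 7-item mean without item 2 would show how far the result depends on the item, but would not recover the true marks. Neither check is planned.

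**Conclusion.** The point holds as a small, avoidable measurement weakness. Correctness on the one free-recall item is judged live, in practice with the time point known, and accepted answers cannot later be re-marked against a strict key. Any extra leniency at post would favour the Aim 1 hypothesis.

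Under the stated assumptions with 40 pairs and SD 0.20, a nominal 5% test would have a false-positive rate of about 5-6% with one-third credit per term and at most 6-15% with full item credit. The scoring rule that decides between these is not stated. The borderline share, acceptance difference, SD, test level and number of completed pairs are all assumed.

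It would go too far to conclude that Aim 1 is invalid or that marking will in fact be lenient: item 2 is one-eighth of one outcome, and the documents show only that accepted answers could not be audited. This is a cheap improvement, not a required correction.

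**What to change.** Change the item 2 instruction so that the interviewer writes every answer word for word at both interviews and does not judge it. Fix one short list of accepted terms beforehand. After data collection, existing study staff code all item 2 answers together from the text, with study ID and time point hidden, and those codes enter the knowledge score. The change has to be in place before baseline interviews, since accepted wording cannot be recovered afterwards.

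The cost is one changed instruction, slightly slower recording, and about an hour to code at most 40 × 2 = 80 short answers. It needs no extra assessor, no extra visit and no change to the planned test.

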Appendix B. Provider/Personnel Pre-Implementation & Post-Implementation Questionnaire

[Interviewer reads each question and answer options to the participant, and records their response on this document. Interviewer can repeat questions and answer options as needed, and answer participants' general questions, but should not provide additional information that would alter the participant's response.]

1.1. Vascular Access Confidence Questionnaire

We would like to know how confident you feel about the dialysis vascular access creation process. For each question, please give an answer between 1 and 10, where 1 is “not at all confident”, and 10 is “very confident”.

1. How confident are you in doing your part to assist your patients through the vascular access creation process?
 - a. Choices: 1.....2.....3.....4.....5.....6.....7.....8.....9.....10
Not at all Somewhat Very

2. How confident are you in knowing how far your patients have progressed in the vascular access creation process?
 - a. Choices: 1.....2.....3.....4.....5.....6.....7.....8.....9.....10
Not at all Somewhat Very

3. How confident are you in your own understanding of the vascular access creation steps?
 - a. Choices: 1.....2.....3.....4.....5.....6.....7.....8.....9.....10
Not at all Somewhat Very

4. How confident are you in your ability to explain vascular access to your patients?
 - a. Choices: 1.....2.....3.....4.....5.....6.....7.....8.....9.....10
Not at all Somewhat Very

5. How confident are you in your ability to explain the vascular access creation process to your patients?
 - a. Choices: 1.....2.....3.....4.....5.....6.....7.....8.....9.....10
Not at all Somewhat Very

6. How confident are you in your ability to help your patients overcome barriers to vascular access creation?
 - a. Choices: 1.....2.....3.....4.....5.....6.....7.....8.....9.....10
Not at all Somewhat Very

7. How confident are you in your ability to communicate with your patients about their emotions surrounding the vascular access creation process?
 - a. Choices: 1.....2.....3.....4.....5.....6.....7.....8.....9.....10
Not at all Somewhat Very

8. How confident are you in communicating appropriate and timely information to other providers about your patients who are going through the vascular access creation process?

a. Choices: 1.....2.....3.....4.....5.....6.....7.....8.....9.....10
Not at all Somewhat Very

9. How confident are you that you are receiving appropriate and timely information from other providers about your patients who are going through the vascular access creation process?

a. Choices: 1.....2.....3.....4.....5.....6.....7.....8.....9.....10
Not at all Somewhat Very

10. How confident are you that you are giving your patients the educational materials and information they need to get through the vascular access creation process?

a. Choices: 1.....2.....3.....4.....5.....6.....7.....8.....9.....10
Not at all Somewhat Very

11. How confident are you that your health care system is set up to support your patients' successful navigation of the vascular access creation process?

a. Choices: 1.....2.....3.....4.....5.....6.....7.....8.....9.....10
Not at all Somewhat Very

Appendix C. Patient Demographic Card

Study ID _____

What is your sex?

- Male
- Female

How old are you? _____ years

What is your racial background?

- African American
- American Indian/Alaskan
- Asian American
- Hawaiian/Pacific Islander
- White
- Other (please describe): _____

What is your ethnicity?

- Hispanic
- Non-Hispanic

What is the highest grade you completed?

- 8th grade or less
- Some high school but did not graduate
- High school graduate or GED
- Some college or 2 year degree
- 4 year college degree or more

What is your household income per year?

- Less than \$25,000
- \$25,000 to \$49,999
- \$50,000 to \$74,999
- \$75,000 to \$99,999
- More than \$100,000

Appendix D. Provider/Personnel Demographic Card

Study ID _____

What is your sex?

- Male
- Female

How old are you? _____ years

What is your racial background?

- African American
- American Indian/Alaskan
- Asian American
- Hawaiian/Pacific Islander
- White
- Other (please describe): _____

What is your ethnicity?

- Hispanic
- Non-Hispanic

What is your job title? _____

How long have you worked in your current role within Geisinger? _____ years

How long have you worked in your current role, including time worked outside Geisinger? _____ years

How long have you been working with...

CKD patients? _____ years

Dialysis patients? _____ years

With patients going through the vascular access creation process? _____ years

Breaking Down Care Process and Patient-level Barriers to Arteriovenous Access Creation Prior to Hemodialysis Initiation

Clinical Trials # NCT04032613

Principal Investigator: [name]

Funded by: NIH/ NIDDK

Statistical Analysis Plan

Version Date: July 19th, 2019

Study participants will complete pre-program implementation and post-program implementation questionnaires to assess the effect of the program on their knowledge of dialysis vascular access and confidence navigating the dialysis vascular access creation process. We will use a paired sample student's t-test to compare participants' pre-program implementation and post-program implementation questionnaire scores. Analyses will be performed in SAS v9.4 and R v3.3.2 or later. Questionnaires are found in the study protocol.
